10.8 Survival

10.8.1 Progression Free Survival

The definition of PFS is the time from randomisation to the first documented disease progression per RECIST v1.1 or death due to any cause, whichever occurs first. This is calculated as:

PFS(days) = (Date of (PD or Censoring) - Date of Randomization) + 1

The event time for PFS will be censored on the date of randomisation with duration of 1 day for;

 Patients lacking any evaluation of disease after first study treatment (unless, they die within 2 scheduled tumour assessments of baseline, this will be treated as an event with the date of death as the event date).

The event time for PFS will be censored at the date of the last available assessment documenting absence of PD for the following scenarios;

- Patients who prematurely discontinue from the study.
- Any PD that occurs immediately after two consecutive missed visits.
- Patients who receive subsequent systemic anti-cancer therapy.
- Patients who are alive and progression-free at the time of a data cut off or End of Study.

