5.2.1.2 Tumour Imaging During the Study

The first on study imaging assessment should be performed at Visit 5 (Week 9 ± 1 week), and then every 6 weeks (± 1 week) through the first year, and every 9 weeks (± 1 week) thereafter for up to 24 months. Tumour assessments will be conducted from the date of randomisation and continue until RECIST v1.1-defined disease progression, irrespective of treatment discontinuation. Any further anti-cancer medication will be recorded until progression.

Imaging timing should follow the planned schedule relative to randomisation and should not be adjusted for delays in cycle starts. Imaging should continue to be performed until radiological progressive disease is confirmed by the investigator, withdrawal of consent, death, or notification by the sponsor, whichever occurs first.

A patient will be determined to have progressed if they have progression of target lesions, unequivocal progression of existing non-target lesions, or the appearance of one or more new lesions during follow-up. Death will be regarded as a progression event in those patients who die before disease progression. Unequivocal malignant disease not identified prior to starting study treatment on additional anatomical imaging (eg, CT, MRI or bone scan confirmed by X-ray) prompted by symptoms, is considered disease progression and should be recorded as new lesions. If progression is uncertain, patients may continue on-treatment until the next scheduled assessment. If an unscheduled assessment is performed, it is important to return to the correct scanning schedule for subsequent scans relative to randomisation, so that the 2 treatment groups are comparable. If the investigator is in doubt as to whether progression has occurred, it is advisable to continue treatment and reassess at the next scheduled assessment, or sooner, if clinically indicated.

To achieve 'unequivocal progression' on the basis of non-measurable disease, there must be an overall level of substantial worsening in non-target disease such that, even in the presence of SD or PR in target disease, the overall tumour burden has increased sufficiently to merit discontinuation of treatment. A modest increase in the size of one or more non-target lesions is usually not sufficient to qualify for unequivocal disease progression status.

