10.9.4 Duration of Response

The DoR is defined as the number of days from the date of first documented CR or PR until the date of first documented PD or death in the absence of PD, whichever is earlier. The number of patients in the FAS with measurable disease at baseline and had a best overall response of CR or PR, will be used.

DoR(days) = (Earliest Date of PD or Death - Earliest Date of CR or PR) + 1

If a patient does not experience PD following an initial CR or PR, then the corresponding DoR will be censored using the same rules defined for PFS (See Section 10.8.1).

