12.5.3.1 Progression Free Survival (PFS)

The key secondary endpoint of PFS will be summarised by Kaplan-Meier plots presented by treatment group. The median, upper quartile, lower quartile PFS and the proportion of patients who are progression-free at 3, 6, and 12 months will be presented along with 80% Wald CIs, obtained using the Brookmeyer-Crowley method (1982). Patients who have not progressed by the time of the data cut-off will be censored following the rules defined in Section 10.8.1.

The comparison between the treatment groups of PFS will be performed by fitting a Cox proportional hazard model (Cox 1975) with treatment group, HPV status (if there are at least 10 patients in each HPV status within each treatment group) and the interaction term between treatment and HPV status (if statistically significant at the 5% level). Efron's method (1977) will be used to handle tied events in any of the independent event intervals. The covariate-adjusted hazard ratio between the treatment groups, based on the profile partial likelihood from the fitted Cox proportional hazards model, will be presented as a measure of the treatment effect along with the respective 80% and 95% Wald CIs and the asymptotic p-value from the Wald test for the difference in the covariate-adjusted log hazards in the fitted model.

If the interaction term between treatment and HPV status is statistically significant, the hazard ratio would be presented separately for HPV+ and HPV- along with the p-value of the interaction term and the 95% Wald CI based on the profile partial likelihood estimate for the interaction effect. Additionally, a Kaplan-Meier plot will be presented by treatment group and HPV status if there are at least 10 patients in each HPV status within each treatment group.

The proportionality of hazards will be examined for the fitted Cox proportional hazards model for PFS using Log-minuslog plots and Schoenfeld residuals. If the proportional hazard assumption is violated between the treatment groups, a modified max combo (Roychoudhury et al 2021) using the Fleming and Harrington 1981 weights (Fleming & Harrington 1981) such as FH(0,0), FH(0.5,0.5), FH(0,0.5), FH(0.5,0) will be implemented for estimating the performance of the competing treatment groups for PFS. The p-value obtained from each of the modified max combo tests will be reported.

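### SAP 10.8.1 and 10.9.4 contradict themselves on death without progression, so such deaths could be censored in PFS and DoR if the wrong sentence is programmed

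*SAP*

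**What the plan says.** **PFS, SAP 10.8.1.** The definition includes death: "The definition of PFS is the time from randomisation to the first documented disease progression per RECIST v1.1 or death due to any cause". The calculation line beneath it does not: "PFS(days) = (Date of (PD or Censoring) - Date of Randomization) + 1". One kind of death is dealt with expressly. A patient with no disease evaluation after first treatment who dies within two scheduled assessments of baseline is an event: "this will be treated as an event with the date of death as the event date". The bullets that censor at the last progression-free assessment include "Patients who are alive and progression-free at the time of a data cut off or End of Study" and, with no qualification, "Patients who prematurely discontinue from the study".

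**PFS, SAP 12.5.3.1.** The analysis section says: "Patients who have not progressed by the time of the data cut-off will be censored following the rules defined in Section 10.8.1". It does not mention patients who have died.

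**DoR, SAP 10.9.4.** The definition ends a response at PD or at death without PD, and the formula takes the earlier of the two dates. The next sentence says: "If a patient does not experience PD following an initial CR or PR, then the corresponding DoR will be censored". It borrows the PFS censoring rules and makes no exception for death.

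**Protocol 5.2.1.2.** "Death will be regarded as a progression event in those patients who die before disease progression".

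**The concern.** A patient who has at least one post-baseline scan and then dies without PD has no PD date to enter in the PFS line. The early-death clause does not apply, because it covers only patients with no evaluation. The cut-off bullet does not apply either, because it requires the patient to be alive.

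The listed rule most likely to catch this patient is the premature-discontinuation bullet. Under Protocol 3.3 a patient completes the study only after tumour assessments up to RECIST progression plus the end-of-treatment and follow-up visits. Someone who dies before PD cannot meet that, and could be recorded as a premature discontinuation and censored at the last progression-free scan. For DoR, the same patient meets the event definition and the censoring trigger at once.

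Censoring these deaths would turn PFS into time to progression with death censored. The Kaplan-Meier curve would then overstate the proportion alive without progression. PFS is a key secondary endpoint with a stated power. No planned analysis would show the problem: SAP 6.1.1 removes the protocol's Fine and Gray competing-risk analysis, and the sensitivity analysis in SAP 12.5.3.4 only drops HPV status.

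**Working it through.** **1. Which text applies to a patient with scans who dies without PD**

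| Text | Treatment of the death |
|---|---|
| SAP 10.8.1 definition | Event |
| SAP 10.8.1 calculation line | Not named |
| SAP 10.8.1 early-death clause | Event, but only for patients with no evaluation |
| SAP 10.8.1 cut-off bullet | Not censored (alive patients only) |
| SAP 10.8.1 premature-discontinuation bullet | Censored, if the death is recorded as a discontinuation |
| SAP 12.5.3.1 | Censored on its face, but refers back to 10.8.1 |
| SAP 10.9.4 definition and formula | Event |
| SAP 10.9.4 censoring sentence | Censored |
| Protocol 5.2.1.2 | Event |

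The adjacent formulas do name death: OS in SAP 10.8.2 and DoR in SAP 10.9.4. The PFS line is the exception.

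**2. The plan's own figure**

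Inputs from SAP 8.1: HR 0.5, two-sided alpha 0.20, about 38 events, power above 80%. Allocation is 1:1 (SAP 8.0). With the Schoenfeld approximation and D events:

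power = Φ( ln 2 × √D / 2 − 1.2816 )

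D = 38: Φ(0.6931 × 6.164 / 2 − 1.2816) = Φ(0.855) = 80.4%. Solving for 80% power gives 38 events, so the plan's figure reproduces.

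**3. Effect on the 6-month PFS estimate (illustration)**

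Assumptions, none of them from the documents: a share f of PFS events are deaths without PD, f is constant over time, and these deaths are censored at the date of death. True 6-month PFS is set at 50%, a round figure. The estimate is then 0.5^(1 − f). The standard error at 25 per arm without earlier censoring is √(0.25/25) = 10 points.

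| f | 0.5^(1 − f) | Shift |
|---|---|---|
| 10% | 53.6% | +3.6 points |
| 20% | 57.4% | +7.4 points |
| 30% | 61.6% | +11.6 points |

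**4. Effect on power (conditional)**

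This arises only if the 38-event trigger counts deaths and the analysis censors them. Events left are 38 × (1 − f), rounded.

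| f | Events left | Power |
|---|---|---|
| 0% | 38 | 80.4% |
| 10% | 34 | 77.0% |
| 20% | 30 | 73.1% |
| 30% | 27 | 69.8% |

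**5. DoR**

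Protocol 1.3 gives a response rate of about 20% with checkpoint inhibitors. In 25 patients that is 0.20 × 25 = 5 responders, so one death handled differently would be a fifth of an arm's data.

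**The case against.** A reader might infer that the SAP removes deaths from both endpoints. The documents do not support that. For PFS, the definition directly above the formula includes death, as do the endpoint in SAP 7.2 and the estimand variable in SAP 9.1.2. The early-death clause shows that a death date can be an event date, and cut-off censoring is limited to living patients. Because Protocol 5.2.1.2 counts death as progression, PD in the calculation line can be read as shorthand. SAP 12.5.3.1 sets no rule of its own, since it refers back to 10.8.1. For DoR, the definition and the formula both name death, and the borrowed PFS rules contain no general scenario that censors a death. All of this stands, and it reduces the point to a contradiction.

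The sizes are also open to challenge. The death shares are assumed. At 10% the shift is under half a standard error. If a PD-only reading were applied to both trigger and analysis, the cut-off would wait for about 38 PD events and nominal power would not change. DoR is not formally compared, and SAP 12.5.4.2 only lists it unless an arm has at least 5 responders. These limits also stand.

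The objection does not dispose of two items. The premature-discontinuation bullet has no exception for death, and the DoR censoring sentence conflicts with the definition in its own section. Neither can be read as shorthand.

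**Conclusion.** The point holds as a contradiction in stated derivation rules. Deaths without PD may be censored in PFS and DoR, depending on which sentence is programmed; it is not shown that they will be. The intended handling is clear from the definitions and from Protocol 5.2.1.2, so the correction is not in doubt.

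If the literal reading were programmed, 6-month PFS would be overstated by about 4 to 12 points for death shares of 10% to 30%. Power would fall to between about 77% and 70% only if trigger and analysis also treated deaths differently. Both ranges rest on assumed shares. The protocol text used here is version 4.0, whereas SAP 6.0 says that the SAP was written against version 5.0. The contradictions within SAP 10.8.1 and 10.9.4 do not depend on that. Severity is minor to moderate.

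**What to change.** - **SAP 10.8.1, calculation line:** *PFS (days) = (earliest date of PD, death or censoring − date of randomisation) + 1*, with a censoring date set only where a listed rule applies.
- **SAP 10.8.1, premature-discontinuation bullet:** state that death is not a premature study discontinuation for PFS or DoR censoring. Without this, the other edits leave the likeliest route to censoring open.
- **SAP 10.9.4, censoring sentence:** *if a patient experiences neither PD nor death following an initial CR or PR, DoR is censored*, keeping the reference to the PFS rules.
- **SAP 12.5.3.1:** refer to *patients who have neither progressed nor died*.
- **Event trigger:** confirm that the count towards about 38 events uses the same event definition as the analysis.

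The cost is SAP wording edits and a check of existing programs. The SAP change history records a Dry Run 1 before version 2.0, so the PFS and DoR derivations may already be coded and should be checked for how they handle deaths without PD. No new data are needed, and the 38-event calculation is unchanged.

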Treatment with pembrolizumab will continue until: RECIST v1.1-defined disease progression is determined by the investigator (Eisenhauer et al 2009), unacceptable toxicity, or a maximum of 24 months. If progression is suspected, but not confirmed, study treatment may continue until confirmation of radiological progression. Treatment with setanaxib or placebo will continue throughout the period of pembrolizumab therapy. When pembrolizumab is discontinued, blinded study treatment will also be discontinued.

Baseline assessments will be performed on Day 1 (Visit 2). Post-Baseline assessments will be performed every 3 weeks up to pembrolizumab discontinuation. Following permanent IMP discontinuation at any time during the study, patients will undergo an End-of-Treatment (EoT) Visit as soon as possible and a Safety Follow-up Visit at 28 days after the last dose.

Initial tumour imaging is performed within 35 days prior to the date of treatment and will be used as the Baseline scan for the tumour assessments. Tumour assessments will then be conducted from the date of randomisation and continue until RECIST v1.1-defined disease progression, irrespective of treatment discontinuation. Efficacy Follow-up for PFS and survival will continue until approximately 38 progression events have occurred. AEs will be recorded up to 28 days after study treatment discontinuation, while any further anti-cancer medication will be recorded until disease progression.

The primary endpoint is best percentage change in tumour size. A population with measurable disease will be selected to generate the maximum tumour response data. The secondary endpoints related to numbers of CAFs, CD8⁺ TILs, and regulatory T-cells in tumour tissue, and gene expression analysis in tumour tissue will be used to demonstrate the underlying mechanisms of action of setanaxib and support the primary objective.

Safety and tolerability data will be regularly reviewed by an unblinded IDMC, with the first assessment after approximately 12 patients (6 per treatment group) have had the opportunity to complete at least one cycle of pembrolizumab +/- setanaxib, followed by periodic assessments at a frequency defined in the IDMC Charter. The IDMC may recommend changes to the setanaxib dose regimen or study conduct based on the safety data reviews.

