9.1.2 Secondary Estimands

The attributes of the secondary estimands are the same as described for the primary estimand in Section 9.1.1 unless otherwise specified in the secondary attributes list below;

Key Secondary Objectives	Secondary Estimand Attributes
 To compare the PFS per RECIST v1.1 in recurrent or metastatic SCCHN patients treated with setanaxib and pembrolizumab versus patients treated with placebo and pembrolizumab 	 Variable: Time from randomisation to the first documented disease progression per RECIST v1.1 or death due to any cause, whichever occurs first. Intercurrent Events: Lacking disease evaluation. Premature study discontinuation Use of certain alternative or additional therapy including a new anti-cancer therapy Strategy: Hypothetical A hypothetical strategy will be applied using censoring rules (see Section 10.8.1). Population Level Summary Measure:
	The HR of PFS between the competing treatment groups.
 To compare the change from Baseline in CAFs level in tumour tissue from recurrent or 	• Variable:

metastatic SCCHN patients treated with setanaxib and pembrolizumab versus patients treated with placebo and pembrolizumab			Change from Baseline in CAFs level in tumour tissue.
			Strategy: Treatment Policy
			A Treatment Policy strategy will address the intercurrent events listed, by considering the intercurrent events irrelevant in defining the treatment effect of interest. The value for the variable of interest is used regardless of whether or not the intercurrent events occur.
• T n tu S p	To compare the change from Baseline in the number of CD8 ⁺ TILs and regulatory T-cells in tumour tissue from recurrent or metastatic SCCHN patients treated with setanaxib and pembrolizumab versus patients treated with placebo and pembrolizumab	•	Variables:
			CD8 ⁺ : Change from Baseline in CD8 ⁺ TILs numbers in tumour tissue.
			T-Cells: Change from Baseline in FOXP3 values.
		•	Strategy: Treatment Policy
			As described for CAFs level above.

Other Secondary Objectives	Other Secondary Estimands

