10.9.3 Objective Response Rate

The ORR (as per RECIST v1.1) is defined as the number (%) of patients with a BOR of CR or PR. The denominator will be based on the FAS, limited to those who have measurable disease at baseline. Patients who discontinue

treatment without PD and go on to have a CR or PR after receiving subsequent systemic anti-cancer therapy will not be considered a responder.

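### The PFS censoring rule for subsequent anti-cancer therapy does not require the therapy to start before PD or death, and does not tie the censoring date to its start

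*SAP*

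**What the plan says.** SAP 10.8.1 defines PFS as "time from randomisation to the first documented disease progression per RECIST v1.1 or death due to any cause, whichever occurs first". It then gives a list of censoring scenarios under this lead-in: "The event time for PFS will be censored at the date of the last available assessment documenting absence of PD for the following scenarios". One entry reads, in full, "Patients who receive subsequent systemic anti-cancer therapy". The next entry does carry a status condition: "Patients who are alive and progression-free at the time of a data cut off or End of Study". Another entry censors a PD that directly follows two consecutive missed visits.

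The PFS estimand in SAP 9.1.2 lists as an intercurrent event "Use of certain alternative or additional therapy including a new anti-cancer therapy". It assigns a hypothetical strategy, to be carried out through the censoring rules of 10.8.1, and adds no timing of its own.

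On data capture, SAP 8.0 says that "any further anti-cancer medication will be recorded until disease progression". Protocol 6.8 has a wider window for medication in general, to the end of Safety/Efficacy Follow-up, and SAP 12.3.2 summarises and lists subsequent systemic regimens. SAP 8.0 and 10.9.1 continue tumour assessments until PD whether or not treatment has stopped.

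**The concern.** Two things are missing from the bullet.

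- **Order.** Nothing says whether PD or the new therapy must come first, and no precedence rule covers a patient who has both. The missed-visits entry shows that the list can override an observed PD, so a programmer cannot assume that a documented PD always stands.
- **Date.** The censoring date is the last scan without PD. It is not the last such scan before the new therapy. Because scans continue until PD, that scan may have been taken on the new therapy.

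PFS is a key secondary endpoint with its own event target. Dropping true progressions would cost power and tend to lengthen the Kaplan-Meier curves. If the share dropped differed between arms, the hazard ratio would be biased. Censoring on new therapy would let that therapy contribute progression-free time, which the hypothetical strategy is meant to exclude.

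**Working it through.** **Literal reading, by example** (hypothetical patients on the protocol scan schedule)

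- *PD first.* Week 9 no PD, Week 15 PD, new therapy at Week 18. The PFS definition gives an event at Week 15. The bullet taken literally gives censoring at Week 9.
- *Therapy first.* Weeks 9 and 15 no PD, new therapy at Week 17, Week 21 no PD, Week 27 PD. The hypothetical strategy points to censoring at Week 15. The bullet taken literally gives Week 21.

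**Reproducing the plan's figure**

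Inputs from SAP 8.0 and 8.1: hazard ratio 0.5, two-sided alpha 0.20, power above 80%, 1:1 allocation. Schoenfeld formula:

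events = 4 × (1.2816 + 0.8416)² / (ln 0.5)² = 4 × 4.508 / 0.4805 = 37.5, rounded up to 38.

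Power with D events = Φ(√D × 0.6931 / 2 − 1.2816). For D = 38: Φ(2.136 − 1.282) = Φ(0.855) = 80.4%. The stated figure reproduces.

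**Conditional loss under the literal reading**

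The share of PFS events that are PDs followed by recorded next-line therapy is not in the documents, so a range is assumed. The calculation also assumes that the cut-off is triggered by reported progressions (SAP 12.5), so removed events are not replaced.

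| Share removed (assumed) | Events left | Power |
|---|---|---|
| 0% | 38 | 80.4% |
| 10% | 34 | 77.0% |
| 20% | 30 | 73.1% |
| 30% | 27 | 69.8% |
| 50% | 19 | 59.1% |

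**Direction of bias**

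An illustrative simulation used 1,000 runs per setting, 25 patients per arm, exponential PFS, control median 3.5 months, true hazard ratio 0.5, protocol scan times and a cut at about the 38th event. These settings are assumptions except the hazard ratio, arm size, scan times and event count. Every event was treated as a PD.

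- With 30% removed in both arms, the median hazard ratio stayed near 0.49 and 71% of runs reached p<0.2, against 81% with none removed.
- With 30% removed on setanaxib and 60% on placebo, the median hazard ratio was about 0.84. With the shares reversed it was about 0.28.
- The setanaxib Kaplan-Meier median rose from 7.6 to 10.4 months at 30% in both arms. The control median stayed at 4.8 months at 30% and rose to 7.6 at 50%.

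**The case against.** A reader might infer that the SAP orders progressors to be stripped of their PFS event. The documents do not support that, and this part of the opposing case stands:

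- PFS runs to the first documented PD or death. Therapy given afterwards does not change that date.
- The estimand treats new therapy as an intercurrent event. Therapy that follows the endpoint is not intercurrent to it.
- Protocol 8.4.2 (version 4.0; the SAP cites version 5.0) gives as its example additional therapy taken before disease progression. It does so under the primary estimand and with a treatment-policy strategy, but the paragraph opens with PFS follow-up.
- The missed-visits entry names the PD to be set aside. The therapy entry names none. The study-discontinuation entry also lacks a time order, so these look like shorthand.
- A patient whose first on-study scan shows PD has no post-baseline scan without PD, so the literal rule gives no clear date.

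Two further inferences also fail. DoR does not share the lost-PD problem: SAP 10.9.4 applies the PFS rules only to responders without PD. Nor is a large power loss established. Further therapy is recorded mainly up to progression, later capture is limited, and some PFS events are deaths, after which no therapy can follow.

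What the objection does not remove is that 10.8.1 is the only operative instruction and omits the order. It also does not touch the date gap, which affects patients whose therapy is recorded because it starts before PD.

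**Conclusion.** The rule is incomplete as written, on both order and date. The likely intent is censoring for therapy started before PD, so this is a wording defect with a damaging literal reading and not a demonstrated loss of events. The 38-event calculation is sound. The power figures of about 77%, 70% and 59% rest on assumed removal of 10%, 30% and 50% of PFS events. The true share is unknown and would be zero if the rule is programmed as probably intended. The hazard-ratio shifts show direction only and depend on shares that differ between arms. The date gap has no size here, because the documents do not say how many patients will start new therapy before PD.

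**What to change.** Replace the bullet in SAP 10.8.1 with: *Patients who start subsequent systemic anti-cancer therapy before documented PD or death are censored at the last evaluable assessment before the start of that therapy; a PD or death that precedes the therapy counts as an event.*

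DoR needs only the date anchor, which it picks up through the cross-reference in 10.9.4.

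The cost is one clause and no new data. It should be settled before unblinding for the primary analysis, because the Cox model for PFS is held for the updated analysis (SAP 12.5) and a choice made after unblinding could look data-driven.
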